Impairments in concentration, memory, and problem solving are also common in PSD and can make it challenging to learn complex social cognitive skills. With this in mind, we developed a social cognitive training that leverages successful methods from bottom-up cognitive remediation to reduce cognitive load and aid with acquisition of social cognitive skills. The training was developed under an NIMH R34 grant and is called Understanding Social Situations (USS). To date, we have developed and refined USS training content, created a treatment manual, conducted a single-arm pilot of the intervention, and collected preliminary data on the effects of USS when incorporated into a psychosocial rehabilitation program. The current proposal is to conduct a fully powered, rigorous randomized controlled trial to test the efficacy of USS versus an active control condition.

4. Significance:

Schizophrenia and other psychotic disorders are among the top 10 causes of disability in the world², with an economic burden of over \$150 billion³. Psychotic disorders are characterized by significant functional disability, including severe impairments in social and community function. Existing treatments fall short of significantly improving social and community functioning, and social re-integration is among the top treatment needs consumers feel are not adequately addressed by existing interventions. If effective, the proposed intervention has the potential to promote rehabilitation and recovery efforts by meaningfully impacting the social lives and wellbeing of Veterans with psychosis.

5. Research Plan:

Overview: We propose a randomized, controlled trial investigating the efficacy of Understanding Social Situations (USS) in improving social functioning in participants with psychotic disorders. We will examine the efficacy of USS on social functioning (primary outcome), real-world social interactions, and social skills. We will also explore moderators and mediators of treatment effects, specifically the impact of baseline variables on treatment

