efficacy and the relationship between USS content knowledge test and social functioning change. One hundred twenty participants will be randomized to two months of individually administered USS or a matched active control training. Comprehensive assessments will occur at baseline, end of training phase, and two-month follow-up, with an additional assessment of the primary outcome and of USS content-related skill (treatment target) at training mid-point. We will additionally obtain baseline-only social function information for a normative (non-psychotic) psychiatric sample, in order to better understand and characterize the patterns of social interactions in our primary psychotic spectrum sample.

Participants:

Psychosis sample: Participants will be Veterans with a psychotic spectrum diagnosis (PSD). Specific inclusion/exclusion criteria will be as follows: diagnosis of psychotic disorder (e.g. schizophrenia, schizoaffective disorder, delusional disorder, psychosis NOS); no prior exposure to USS training, age 18 and

over; not meeting criteria for substance use disorder in past 30 days; psychiatric stability as evidenced by minimum of 30 days since last psychiatric hospitalization and since last change in psychiatric medications; no evidence of developmental disability in chart or on baseline assessment; no severe, uncorrected auditory/visual impairment; no diagnosis of medical or neurological illness known to impair brain function including dementia, presence of seizures, history of head trauma with loss of consciousness > 1hr, or clear cognitive sequelae from other illness or injury, per medical chart review; fluency in English; ability to provide legal written informed consent (i.e. the participant does not have a conservator); not currently enrolled in another treatment study targeting, or expected to impact, functioning. We hope to randomize approximately 120 Veterans into the study conditions.

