Psychiatric control sample: Specific Inclusion/exclusion criteria for the psychiatric control group: age 18 and over; currently receiving mental health treatment; no lifetime diagnosis of psychotic disorder (e.g. schizophrenia, schizoaffective disorder, delusional disorder, psychosis NOS) based on clinical interview; not meeting criteria for PTSD in the past 30 days based on clinical interview; not meeting criteria for substance use disorder in past 30 days based on clinical interview; not meeting criteria for a major depressive or manic episode in the last 30 days based on clinical interview; psychiatric stability as evidenced by minimum of 30 days since last psychiatric hospitalization, no current high risk for suicide flag on their chart, and no active suicidal or homicidal ideation in that past 30 days; no evidence of developmental disability in chart or on baseline assessment; no severe, uncorrected auditory/visual impairment; no diagnosis of medical or neurological illness known to impair brain function including dementia, presence of seizures, history of head trauma with loss of consciousness > 1hr, or clear cognitive sequelae from other illness or injury, per medical chart review; fluency in English; access to a smartphone to which they are willing to receive surveys via text message; ability to provide legal written informed consent (i.e. the participant does not have a conservator); We hope to have approximately 20 participants complete study procedures.

Measures for primary psychotic-spectrum sample:

Baseline assessments will consist of demographic, intelligence, psychiatric, cognitive, social function and knowledge of USS training content measures. Post-training and 2-month follow-up assessments will mirror baseline assessments, with the exception of diagnostic interviews and IQ estimate, which will only be administered at baseline. An additional assessment of the primary outcome, SFS, and of the proposed mediator of treatment effects, USS Skills Test, will occur at treatment mid-point. Please refer to Assessment Timeline below. The baseline assessment will be split into a screening assessment to confirm study eligibility (demographics, WASI, SCID, SFS), and a subsequent baseline assessment for those who pass the screening (PANSS, PHQ-9, QLS, MCCB, SSPA, USS Skills Test)

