Intelligence: The Wechsler Abbreviated Scale of Intelligence (WASI⁶⁸, 2-subtest estimate) will be used to obtain estimates of current intelligence (IQ Estimate score). The WASI 2-subtest IQ estimate correlates highly ($r=.87$) with the Wechsler Adult Intelligence Test⁶⁹, the most commonly used and accepted measure of intellectual function. It also has high internal consistency reliability ($r=.93$ for adult sample), and 2-12 week test-retest stability ($r=.85$). The WASI will be used to characterize the study sample and screen for intellectual disability (IQ < 70) at baseline.

Diagnostic and Symptom: The Structured Clinical Interview for DSM-V (SCID⁷⁰) will be used to confirm psychotic spectrum diagnoses. The SCID is the most commonly used semi-structured interview for obtaining DSM-V diagnoses. Modules A through E will be used to determine presence of psychotic and mood syndromes, substance use history, and differential diagnosis. The Positive and Negative Syndrome Scale (PANSS⁷¹) will be used to characterize participants by assessing the presence and severity of psychiatric symptoms. The PANSS is an interviewer-rated scale indexing the core symptoms of psychosis as well as a broad range of general psychiatric symptoms *including depression and anxiety*. Each symptom is rated on a Likert-type scale ranging from 1-7, for total score range of 30 to 120. Initial reports using this scale provide evidence of good internal reliability for the three subscales ($\alpha = .73$ to $.83$), with adequate test-retest reliability over 3-6 month inpatient phase ($r=.60$ to $.80$) and good interrater reliability ($r=.83$ to $.87$). Within our research group, ICC's against gold standard, study PI, range from $.85$ -.97 for PANSS components. For initial exploratory analyses of symptom severity as a potential moderator of treatment effects, PANSS Total Score will be used. As warranted, subsequent analyses may examine the Positive, Negative, and General symptom

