In-person study visits conducted at baseline, post-training and follow-up time points will kept as brief as possible, and include the following safety guidelines:

- For any in-person visits that take place, one day prior to the visit and/or at time of visit, participants will be asked the standard COVID-10 screening questions in place at VACHS, and be asked to use a hand sanitizer upon entering the office.
- Participants will be required to wear a 2-ply face mask when in the room with research staff, and if they do not have one, one will be provided for them.
- Staff will utilize masks, gloves, face shields and social distancing during study visits, and will sanitize the office between each in-person visit and at the end of the day.

Recruitment: Veterans with and without psychotic spectrum diagnoses will be recruited from VACHS outpatient clinics via flyers, presentations of study to treatment teams, other research groups, and MH clinicians. The study will also be presented to Veterans during community meetings of the VACHS Psychosocial Rehabilitation and Recovery Center, which serves Veterans with serious mental illness. Recruitment will also

occur through our re-contact repository (those who have participated in our group's prior studies and agreed to be re-contacted with information about additional research opportunities), with the exception of those who participated in the initial USS treatment development trial. We may also pull MH clinic appointment lists, screen upcoming appointments for potential eligibility, alert providers to upcoming appointments with potentially eligible participants, and ask that they refer those who are interested in learning more about the study. We will also offer a small incentive to past/current participants who refer other eligible Veterans. For Veterans with psychotic spectrum diagnoses only, we may also send out study solicitation letters (with opt-out cards), as has previously been approved by the HSS.

Randomization for psychotic spectrum sample: Veterans who meet eligibility criteria and consent to study participation will be randomized to receive either USS or AC in a 1:1 ratio. Randomization will be stratified by baseline SFS score, using a permuted block design with variable block size. The randomization scheme will be computer-generated by the statistician and the allocation sequence will be concealed.

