Analysis of Primary Outcome SFS (Aim 1): The primary objective of the analysis is to demonstrate that USS will improve social functioning at the end of training more than active control in participants with PSD and impaired social functioning. The primary outcome (total scores on the SFS) will be assessed prior to initiation of intervention (pre), the training mid-point (mid), the end of training (post) and 2 months following the end of training (FU). Likelihood-based ignorable analysis using a linear mixed model will be used to compare social functioning between groups^{85, 86}. The primary advantage of the repeated measures linear mixed model when compared to commonly used methods such as complete case analysis and single imputation (e.g. last observation carried forward) is its flexibility in handling missing data. This analysis will assume that missing data occurs at random (i.e. MAR, not informative). The inclusion of pre, mid and FU outcome data in the model will assist in meeting this assumption. Furthermore, we will evaluate patterns of missing data as well as determine baseline characteristics that are predictive of dropout. If identified, these characteristics will be included in the model to meet the MAR assumption. The mixed model will include fixed effects for intervention (USS vs. active control), time (mid, post, FU), and the interaction of intervention with time. An additional fixed effect will be included for baseline SFS at pre. An unstructured covariance pattern will be used to accommodate correlation from repeated measures. A linear contrast will be used to estimate intervention group differences and 95% confidence intervals at the post assessment.

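### Does the primary result get attached to a population with impaired social functioning that the eligibility criteria never select?

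*Combined protocol and SAP*

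**What the plan says.** Under Analysis of Primary Outcome SFS (Aim 1), the objective is to show that "USS will improve social functioning at the end of training more than active control in participants with PSD and impaired social functioning". Under Measures for primary psychotic-spectrum sample, the baseline work is divided into a "screening assessment to confirm study eligibility (demographics, WASI, SCID, SFS" and then "a subsequent baseline assessment for those who pass the screening". Under Participants, the list opens with "Specific inclusion/exclusion criteria will be as follows: diagnosis of psychotic disorder" and goes on through prior USS exposure, age, substance use, psychiatric stability, developmental disability, sensory impairment, neurological illness, English fluency, consent and enrolment in other treatment studies. Nothing in it refers to SFS, the Quality of Life Scale or any level of functioning.

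The Overview describes a trial "investigating the efficacy of Understanding Social Situations (USS) in improving social functioning in participants with psychotic disorders", with no impairment qualifier. Baseline SFS has a second stated use before allocation: "Randomization will be stratified by baseline SFS score, using a permuted block design with variable block size".

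**The concern.** Read together, three places seem to describe different trials. The objective names an impaired population, the screening text implies that SFS can decide who enters, and the criteria admit any SFS level. The IQ test shows the contrast: it is used to "screen for intellectual disability (IQ < 70) at baseline", a stated cut-off that serves the listed developmental-disability criterion. SFS is the only screening instrument that serves no listed criterion.

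Two harms could follow. If no SFS threshold is applied, Veterans with little room to improve are randomized, the average effect could fall below the 9 points used for sizing, and the result might still be reported as applying to impaired participants. If an unwritten threshold is applied, the published criteria do not describe who was eligible.

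**Working it through.** **1. The plan's own figure.** Inputs from Justification of Sample Size: difference 9, SD 13.1, two-sided alpha 0.05, power 90%, 1:1 allocation.

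- Effect size: 9 / 13.1 = 0.69, as stated.
- Normal approximation: n = 2(1.960 + 1.282)² × 13.1² / 9² = 44.5, so 45 per group.
- Exact two-sample t test (noncentral t): 45 per group gives power 0.897 and 46 gives 0.903, so 46 per group, as stated.
- Dropout: 92 / 0.8 = 115, and 120 are planned. The plan could lose 1 − 92/120 = 23.3% and still keep 92.

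The sizing reproduces, and it uses no impairment criterion.

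**2. Which population does each place imply?**

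| Place | Impairment restriction? |
|---|---|
| Purpose, Aim 1 and H1.1 | No |
| Research Plan, Overview | No |
| Participants, psychosis sample | No |
| Sample-size hypothesis | No |
| Primary mixed model | No; baseline SFS is a covariate |
| Lead-in sentence of the Aim 1 analysis | Yes |
| Screening list | SFS named, no threshold |

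The qualifier stands once, in a lead-in sentence. Nothing that determines who is randomized or how the contrast is estimated uses it.

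**3. Why is SFS collected at screening?** Demographics serve the age criterion, the IQ test serves developmental disability, and the diagnostic interview serves diagnosis and substance use. SFS serves stratification, so its value must exist before allocation. That explains its early collection without any hidden cut-off. The word eligibility is then loose for this one item.

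**4. The dilution argument.** Assume a share f of participants is unimpaired and gains nothing over control. The mean difference becomes 9(1 − f). Power is at 46 per group. The adjusted columns use residual SD 13.1 × √(1 − r²), where r is an assumed baseline-to-post correlation that the documents do not give: 11.34 at r = 0.5 and 9.36 at r = 0.7.

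| f | Difference | Unadjusted | r = 0.5 | r = 0.7 |
|---|---|---|---|---|
| 0 | 9.0 | 90% | 96% | 99% |
| 0.1 | 8.1 | 84% | 92% | 98% |
| 0.2 | 7.2 | 74% | 85% | 96% |
| 0.3 | 6.3 | 63% | 75% | 89% |

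The arithmetic is right, but its starting point is not in the documents. The 9 points is presented as a clinically meaningful difference, not as the effect expected among impaired participants. The SD comes from preliminary data that are not described as restricted to impaired participants. The share f and the zero gain are both assumptions. The primary model adjusts for baseline SFS, so the unadjusted column overstates any loss if baseline and post scores are correlated.

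**5. What would rewording change?** Dropping the qualifier and the eligibility label leaves the same participants, model, contrast and power. The power figures therefore cannot be a reason for the edit.

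**6. Is dependence on baseline SFS already covered?** The assessment table labels SFS a potential moderator as well as the primary outcome. Analysis of Moderation (Exploratory Aim B) tests interactions with baseline characteristics inside the longitudinal model. Its list of examples does not name SFS, but the list is open.

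**The case for a change.** The best case for acting is that the qualifier is joined by a conjunction and so reads as an extra condition. The Background calls social impairment prominent in psychosis, which is not the same as universal. The screening text says eligibility in plain terms, and a reader cannot tell from the documents whether anyone may be turned away on SFS. Covariate adjustment improves precision but does not restrict the population. Only the sponsor can say which reading is intended.

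Most of this stands as a comment on wording: impairment is not ensured in the randomized sample, and the three places could be worded to agree. It does not show that the enrolled population differs from the one described. The documents give no baseline SFS distribution and no definition of impaired. The Background treats functional disability as a defining feature of these disorders, so the phrase can also be read as describing the condition. That a report would claim an effect in a selected impaired group is a prediction about reporting; the aims already state the broader population. An unwritten threshold is conjecture, and if one exists, listing it would record a detail without altering the comparison.

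**Conclusion.** No change to the plan follows. The inconsistency is clerical: one qualifier in a lead-in sentence and one loose label in the screening list, set against aims, criteria, sizing and model that all describe Veterans with psychotic disorders at any SFS level. The randomized comparison is valid for whoever is enrolled, and the conclusion under Aim 1 is sound for that population. An analyst following the plan would fit the same model to the same participants under either wording. The effect on the primary estimate, its confidence interval and the required 46 per group is nil.

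This rests on reading the listed criteria as complete, which is how the Participants section presents them, and on SFS being taken at screening to supply the stratification value. The documents support the second reading but do not state it. The fall in power to between 84% and 63% should not be relied on, because neither the unimpaired share nor the zero gain comes from the documents.

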Justification of Sample Size: The primary hypothesis is that USS will result in greater total SFS scores immediately following training (i.e. 'post' assessment) compared to control. We have powered our study to detect what we consider a clinically meaningful, moderate effect on this measure. Given the following: 1) power of 90%, 2) a two-sided 0.05 significance level, 3) a standard deviation for total SFS score of 13.1 (from our preliminary data), and 4) a 1:1 intervention allocation, a sample size of 46 subjects per group will be required to detect a 9 point difference (i.e. moderate effect size $d=0.69$) between USS and control in total SFS score at the post assessment. Please refer to Figure, showing the power to detect different effect sizes in total SFS given this sample size. A total of 120 participants will be enrolled and randomized to accommodate up to 20% dropout.

While inherently difficult to define as it varies by perspective (e.g. researcher, consumer, insurance company)⁸², we settled on moderate ES on SFS as clinically meaningful based on past social cognitive studies that used the SFS and noted that improvement in social relationships (more friends, less time spent alone, higher quality of social communication) were observed with small-medium effect sizes⁸³. Small-medium effects on the SFS have also been related to greater social acceptability by peers, better overall social skills ability, and higher medication compliance, with effects greater than 0.50 on social cognitive measures distinguishing between patients with psychosis and higher functioning patients with bipolar disorder⁸⁴. Perhaps the most striking example of the real-world significance of change on the SFS comes from the original SFS validation study, wherein 11 point difference separated those who were employed from those who were not⁷³.

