General Approach: Nominal and ordinal categorical variables will be summarized using frequencies and percentages. Continuous variables will be summarized with the following descriptive statistics: N, mean, standard deviation, median, minimum, maximum, interquartile range, and range. No imputation of missing data will be performed in the primary and secondary analyses. Diagnostic tests and sensitivity analyses will be performed. Parametric distributional assumptions will be checked. If assumptions fail, other distributions will be considered prior to transformations and non-parametric methods. For all analyses, two-sided significance tests will be implemented and will be performed using SAS v9.4 (Cary, NC).

Comparability of Baseline Characteristics: Distributions of baseline demographic and clinical characteristics will be summarized. Comparability for continuous variables will be examined graphically and by summary statistics (means, medians, quartiles, etc.). Categorical variables will be examined by frequency distributions.

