Plan for Missing Data: Several strategies will be imposed to accommodate the likelihood that missing data will occur during this study. Prevention is the most obvious and effective manner to control bias and loss of power from missing data⁹². Prior to the trial we will pilot data collection procedures. Variables with large proportions of missing data will be excluded from collection. We will follow the intent to treat principle, requiring follow-up of all participants randomized regardless of the treatment received⁹³. Regular data entry into case report forms (CRFs) combined with monitoring and missing data reports will trigger protocols for tracking and obtaining missing data. Despite these prevention efforts it is reasonable to assume missing data will occur. Our proposed primary and secondary analyses make use of all available data and are valid under the assumption that missing data will be missing at random (MAR)^{86, 94}. We will evaluate the plausibility of this assumption by determining the extent of missing data and use logistic regression to identify factors associated with missing data. We will conduct sensitivity analysis using a pattern-mixture approach implemented using multiple

imputation under missing not at random (MNAR) assumptions to examine the robustness of conclusions of the primary analysis to missing data^{86, 92}.

6. References:

1. World Health Organization. Schizophrenia: Fact sheet No 397.; Sept 2015.
2. National Institutes of Mental Health. [Archive Material] Translating behavioral science into action: report of the national advisory mental health council behavioral science workgroup; 1999.
4. American Psychiatric Association TFoD-V. Diagnostic and statistical manual of mental disorders, fifth edition. Arlington, VA: American Psychiatric Association; 2013.

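### Does adding dropout predictors to the primary SFS model, or allowing another distribution, leave the confirmatory analysis open?

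*Combined protocol and SAP*

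**What the plan says.** Under Analysis of Primary Outcome SFS (Aim 1), the primary model is a repeated-measures linear mixed model. Its fixed effects are intervention, time (mid, post, FU), their interaction and baseline SFS. The covariance is unstructured, and a linear contrast gives the group difference at post with a 95% confidence interval. The team will also look at missing-data patterns and at which baseline characteristics predict dropout. On those it says: "If identified, these characteristics will be included in the model to meet the MAR assumption".

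The Plan for Missing Data states that the team will "use logistic regression to identify factors associated with missing data", as a way of judging whether MAR is plausible. It adds an MNAR pattern-mixture sensitivity analysis by multiple imputation.

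The General Approach, which covers every outcome, says: "If assumptions fail, other distributions will be considered prior to transformations and non-parametric methods".

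None of these sections lists candidate characteristics, sets a cut-off or a cap, dates the decision or names an alternative distribution. They do not say whether the step is done blind to arm.

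**The concern.** A confirmatory test should not depend on decisions taken once results can be seen. Here two parts of the primary model depend on the data, and neither has a written criterion.

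The pool of possible dropout predictors is long: demographics, IQ estimate, PANSS and its subscales, PHQ-9, QLS and its domains, MCCB, SSPA and the Skills Test. At the planned ceiling of 20% dropout, only 0.20 × 120 = 24 dropouts inform the screen, so much of what it selects could be noise. A covariate that predicts dropout but not SFS does nothing for MAR.

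Two statisticians could follow the text and reach different primary estimates. If the more favourable one could be chosen, the 5% error rate would not hold. A move to ranks or a transformation would also leave the mean-difference scale on which the trial is powered.

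**Working it through.** **The plan's own figure.** Inputs from Justification of Sample Size: "2) a two-sided 0.05 significance level", power 90%, SD 13.1, difference 9 points, 1:1 allocation.

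- Effect size: 9/13.1 = 0.687, stated as 0.69.
- Normal approximation: n = 2 × [(1.960 + 1.282) × 13.1/9]² = 44.5, so 45 per group.
- Noncentral t: 46 per group, power 0.903. This matches "a sample size of 46 subjects per group will be required".
- Dropout: 92/0.80 = 115, and 120 covers it. With 20% loss, 120 × 0.80 = 96 remain (48 per group), power 0.915.

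The concern alters none of these figures.

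**How often would a covariate enter by chance?** If no candidate truly predicts dropout and candidates are independent, P(at least one) = 1 − (1 − a)^k. The documents give neither k nor a, so both are assumed:

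| Candidates k | a = 0.05 | a = 0.20 |
|---|---|---|
| 5 | 22.6% | 67.2% |
| 10 | 40.1% | 89.3% |
| 20 | 64.2% | 98.8% |

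With 20 candidates at 0.05, the expected number of false entries is 20 × 0.05 = 1. Scales and their own subscales are correlated, which lowers the chance. With 20 candidates, 24 dropouts and equal pairwise correlation (an assumption), simulation gives 64% at r = 0, 55% at 0.3, 42% at 0.5 and 29% at 0.7. One irrelevant covariate raises the variance of the treatment estimate by only about 1% at 96 completers.

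**Does chance entry matter?** Simulation set-up, all assumed except N and dropout: 120 randomised, 20% dropout completely at random, an ANCOVA at post in place of the full mixed model, baseline-to-post correlation 0.6, 5 to 20 weakly prognostic covariates (0.12 to 0.20 each), cut-offs 0.05 and 0.20, 5,000 null runs per setting (Monte Carlo SE about 0.003) and 3,000 per setting with a true effect.

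| Quantity | Result |
|---|---|
| Type I error, fixed model | 0.047 to 0.057 |
| Type I error, dropout rule followed | 0.048 to 0.061 |
| Verdict differs between the two, null | 0.6% to 2.8% |
| Verdict differs, d = 0.35, 10 candidates | 2.5% to 8.2% |
| Verdict differs, d = 0.69, 10 candidates | 0.2% to 0.7% |
| SD of the shift in the estimate | about 0.3 to 0.8 SFS points |

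The largest shift SD is 0.8/9 = 9% of the design difference. The rule selects on dropout, not on the treatment p-value, which is why the error rate barely moves. A second simulation under the rule (10 candidates, one prognostic, about 20% dropout) gave 0.049 to 0.053.

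**What would locking the model do?** In an assumed scenario where a prognostic covariate drives dropout in one arm only, the model without added covariates was biased by about 1.1 SFS points (1.1/9 = 12% of the design difference), with type I error about 0.08. Under the plan's rule the bias was 0.05 to 0.24 points and type I error 0.053.

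**The case for a change.** The strongest case for a change is that the text permits discretion even if it does not invite it. PANSS total, subscales, depression and anxiety (6), QLS total and domains (5), MCCB composite and domains (8), plus WASI, PHQ-9, SSPA and the Skills Test (4), make 6 + 5 + 8 + 4 = 23 candidates before demographics. The plan does not say that the choice is made blind to arm. If an analyst could report the better of the fixed and covariate-added models, type I error would be 0.051 to 0.073. With rank versions of both also open, it would be 0.066 to 0.090. Taking the smallest p over many covariate sets and a rank analysis reaches about 11%.

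Those figures describe choosing by p-value, which the plan does not provide for. Its wording makes the model with identified predictors the primary one, so there is no adjusted-or-unadjusted choice to exploit. The screen itself needs only baseline data and dropout status, so it can be run on pooled data. The distribution sentence is a general rule for all outcomes, with transformations and non-parametric methods placed last. For SFS the Aim 1 section itself specifies a linear mixed model.

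A second argument is that an added covariate with missing values would remove participants, because the primary analysis uses no imputation and the remote procedures drop or replace some MCCB tests. That is worth an analyst's attention. However, baseline assessment precedes randomisation, and no rate of missing baseline data is given from which to size a loss.

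Two points stand: the list, cut-off and timing are unwritten, and a marginal result could cross 0.05 in a small share of trials.

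**Conclusion.** The concern does not call for a change. The plan leaves detail unstated, but the primary model is identifiable: its core is fixed and the covariate rule is a directive. Followed as written, the rule shows no material inflation of type I error (0.048 to 0.061 against 0.047 to 0.057). It moves the estimate by well under one SFS point in SD terms and almost never alters the verdict at the effect the trial is powered for. Sensitivity is greater for smaller effects, up to 8.2% of trials at d = 0.35 with the loose cut-off.

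The alternative, barring added covariates and sending dropout predictors only to the MNAR sensitivity analysis, is a trade-off and not a clear gain. It would take from the MAR-based primary analysis the variables meant to support that assumption. The candidate list, cut-off and distributional check are details a competent analyst would settle before comparing arms, and the model without the added terms can be shown alongside.

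The conclusion rests on the simulation assumptions: 5 to 20 candidates, cut-offs of 0.05 and 0.20, weakly prognostic covariates and a single-visit ANCOVA standing in for the mixed model. It also rests on the rule being followed as written, not used to choose among results.
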